3.2 Outcome Variables

3.2.1 Primary Outcome Variables

The primary outcomes for this pilot RCT will relate to feasibility of recruitment and retention. For recruitment, we will describe the number of patients screened vs. the number of patients eligible; the number of patients eligible vs. the number enrolled; and the hospital day of enrollment (in relation to the admission and discharge dates). For retention, we will describe the number of participants in the intervention group for whom we are able to deliver the full enhanced opioid stewardship intervention, as well as the number in intervention and control groups who complete the peri-discharge evaluation.

3.2.2 Secondary and Exploratory Outcome Variables (if applicable)

A secondary outcome for this pilot RCT will include a count of guideline-based care elements considered to be “best practices” for opioid stewardship in the setting of chronic pain. These include ordering of alternative pain relief medications (e.g., acetaminophen), ordering of a bowel regimen, ordering of medication to treat opioid use disorder, order of urine toxicology screen, ordering of ECG for patients prescribed methadone, avoidance of co-prescriptions of benzodiazepines, and other associate “best care” practices. These metrics will be abstracted from the medical record.

Other secondary outcomes will include pain frequency, intensity, and interference, assessed using a modified Brief Pain Inventory.¹ Depression and anxiety will be measured using the Patient Health Questionnaire-4.² Participant satisfaction with pain care will also be assessed

at discharge. ED visits and readmissions at the 30 days post-discharge from the hospitalization in which the participant is recruited will also be abstracted from the medical record.

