2.1 Hypothesis

Participants randomized to the intervention will have less pain, fewer opioid-related adverse events, and greater improvement in quality of life compared with control participants, as measured at hospital discharge.

The care of intervention participants will also include a greater number of guideline-based care elements for opioid stewardship compared with the care of control participants, as measured at hospital discharge.

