3.4 Study Procedures

All patients will receive standard hospital care. Patients who are identified as eligible for the study via screening in Epic will be approached during hospitalization, undergo informed consent, and be enrolled in the study. Those who consent will be asked questionnaires

related to patient reported outcomes of pain, anxiety, depression and quality of life at baseline. Patients will then be randomized on a 1:1 ratio to either the enhanced opioid stewardship program arm or a control (i.e., usual care) arm. Patients who are randomized to the intervention arm will have their medical record reviewed by both a pharmacist and a physician trained in pain and addiction medicine. The pharmacist and physician will provide best practice guidance via an Epic note to the primary care teams to consider, versus continuation with their usual care plan. All guidance will be voluntary for clinical teams to follow. All participants will be tracked daily in Epic for discharge status, and when discharge within 48 hours is anticipated, the study team will perform the final patient interview, which will be very similar to the baseline interview and composed of questionnaires related to pain, anxiety, depression, and quality of life. Medical record abstraction will be performed to abstract relevant characteristics of each participant's hospitalization, use of guideline-based best practices for pain management and opioid stewardship at discharge, and incidence of readmissions and ED visits within 30 days after discharge for the hospitalization during which the participant was recruited.

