3.5 Study Schedule

The total number of visits as part of this intervention will include (1) screening and consent, (2) baseline interview (may be combined with consent visit, per participant's preference), and (3) a peri-discharge interview (within 48 hours of anticipated discharge). The total number of study visits is expected to be three per participant, with the potential for greater frequency of interaction via phone. Each visit will last approximately 30 minutes or less.

Study Schedule:

Study Activity	Time frame/duration
1. Currently hospitalized patients screened in Epic	Every weekday
2. Eligible participants approached by study team	Every weekday
3. Study described, questions answered, written informed consent obtained	30 minutes
4. Participant completes baseline interview; \$25 gift card provided	15 minutes
5. Participant randomized to intervention or usual care arm	1 minute
6. Participant's hospitalization tracked for anticipated discharge status	Daily
7. Intervention participants' charts reviewed by study team's addiction medicine physician/pharmacist for adherence to best practice guidelines for pain management/opioid stewardship.	Once, within 24 hours of randomization
8. Study addiction medicine physician composes note in intervention participant's medical record with recommendations to optimize guideline-based pain management/opioid stewardship	Once
9. Study addiction medicine physician alerts primary clinical care team via Mobile Heart Beat of Epic note regarding guideline-based care recommendations	Once
10. Final participant interview performed within 48 hours of anticipated discharge; \$25 gift card provided	15 minutes
11. Medical record abstraction performed for hospitalization characteristics, use of guideline-based best practices for pain management/opioid stewardship, and readmissions/ED visits within 30 days	1-30 days post-discharge

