3.6.3 Study Visits (if applicable)

There will be up to 3 study visits with each participant, which will take place during hospitalization or in the first week after hospital discharge.

The first study visit will be for recruitment and enrollment. This visit will follow the format described in Section 3.6.2. This visit will last approximately 30 minutes.

The second study visit will be for completion of the baseline interview. This study visit may occur directly after enrollment. During this interview, participants will be asked questions related to pain, depression, and anxiety. Pain will be assessed using an abridged version of the Brief Pain Inventory,¹ which will take 5 minutes to complete. Depression and anxiety will be assessed with the Patient Health Questionnaire-4,² which will take 2 minutes to complete. They will also be asked demographic questions, for descriptive purposes. The baseline interview visit will last approximately 15 minutes.

The third study visit will be for completion of the final interview, which will take place within 48 hours of anticipated discharge. Participants will answer questions identical to those asked in the baseline interview on pain, depression, and anxiety. They will also be asked one question regarding their satisfaction with pain: "How pleased are you with your pain outcome during this hospital visit?", which will be answered on a Likert-type scale. The final interview will last approximately 15 minutes.

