3.7.3 Planned Analyses

Due to the pilot nature of this trial, statistical considerations will consist primarily of bivariate analyses (i.e., t-tests, rank sum, and chi-square tests, as appropriate to variable type) to ensure balance of covariates between randomization groups and also to explore unadjusted associations between randomization groups and our outcomes. Exploratory regression analyses may be utilized to evaluate multivariable-adjusted associations between randomization groups and our outcomes, particularly if an imbalance between covariates among randomization groups is discovered.

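### The guideline-care count has no stated window start and no count at randomization in both arms, so its unadjusted comparison gives up precision that one extra chart time point would partly recover

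*Combined protocol and SAP*

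**What the plan says.** Section 3.2.2: "A secondary outcome for this pilot RCT will include a count of guideline-based care elements". The count is taken from the medical record. The listed elements include "order of urine toxicology screen, ordering of ECG for patients prescribed methadone, avoidance of co-prescriptions of benzodiazepines", together with non-opioid analgesics, a bowel regimen, medication for opioid use disorder (OUD) and an open-ended remainder.

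On timing, section 2.1 expects a "greater number of guideline-based care elements for opioid stewardship compared with the care of control participants, as measured at hospital discharge", and section 3.4 abstracts "use of guideline-based best practices for pain management and opioid stewardship at discharge". Both give the end of the window. Section 3.5 says when the abstraction is done (1–30 days after discharge), not which orders count.

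On data at randomization:
- **Baseline interview (3.6.3):** "During this interview, participants will be asked questions related to pain, depression, and anxiety", plus demographics.
- **Chart review near randomization (3.5, item 7):** the charts of intervention participants only are reviewed by the "physician/pharmacist for adherence to best practice guidelines for pain management/opioid stewardship". This is part of the intervention.
- **Study records (4.6):** the abstraction forms listed are post-discharge and 30-day forms.

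On analysis, section 3.7.3 plans bivariate tests to "explore unadjusted associations between randomization groups and our outcomes". It adds: "Exploratory regression analyses may be utilized to evaluate multivariable-adjusted associations between randomization groups and our outcomes", particularly if covariates turn out imbalanced. No covariate is named. Section 3.7.1 repeats this.

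**The concern.** Two linked gaps affect the outcome on which the intervention acts most directly.

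**The window.** For an element scored by its status at discharge, no start is needed. For a one-time order it is. If a urine toxicology screen was sent on admission, before enrollment, two abstractors could score it differently and both comply with the protocol.

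**The missing covariate.** The hospital day of enrollment is itself a feasibility outcome (3.2.1), so it is expected to vary. Some patients will already have several elements in place when randomized, others none. Randomization balances this in expectation, so the difference in mean discharge counts is unbiased. The prior elements still add between-patient variation. A count at randomization would explain part of it, but none is planned. The permission to run adjusted regression does not supply that covariate.

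Section 3.7.2 disclaims power, and the trial is mainly about feasibility. However, guideline-based care is one of two secondary objectives (2.3), and section 4.15 intends the results to support later grant applications. A narrower interval from the same 100 patients serves that use better.

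**Working it through.** **Inputs from the documents.** 100 participants randomized 1:1 (3.3.1, 3.4), so 100 / 2 = 50 per arm, as section 3.3.1 states. There is no power, SD or precision figure to reproduce (3.7.2).

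**General formula.** Unadjusted, in SD units: SE = √(2/50) = 0.200, and 95% half-width = 1.96 × 0.200 = 0.392 SD. If the randomization count has within-arm correlation ρ with the discharge count, regression on it multiplies the variance by about (1 − ρ²), before a cost of about 1% for one degree of freedom. The unadjusted total N of equal precision is 100 / (1 − ρ²).

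| ρ (assumed) | 95% half-width (SD) | Equivalent unadjusted N |
|---|---|---|
| 0 | 0.392 | 100 |
| 0.3 | 0.374 | 110 |
| 0.5 | 0.339 | 133 |
| 0.7 | 0.280 | 196 |

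**What ρ might be.** The rates here are assumptions. Four elements apply to everyone, OUD medication to 30% and ECG to 15%, giving 4 + 0.30 + 0.15 = 4.45 applicable elements on average. A share *s* is in place at randomization. Of the unmet elements, 20% (control) or 40% (intervention) are newly met by discharge. Elements are independent.

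*One cell by hand: s = 0.30, none lost.*
- Probability that an applicable element is met at discharge: control 0.30 + 0.70 × 0.20 = 0.44; intervention 0.30 + 0.70 × 0.40 = 0.58.
- Variance of the count, control: 4(0.44)(0.56) + (0.132)(0.868) + (0.066)(0.934) = 1.162. Intervention, in the same way: 1.198. Mean 1.180.
- Unadjusted half-width: 1.984 × √(2 × 1.180 / 50) = 0.431.
- Variance of the randomization count: 4(0.30)(0.70) + (0.09)(0.91) + (0.045)(0.955) = 0.965.
- Covariance of the two counts, control: 4(0.30)(0.56) + 0.09(0.868) + 0.045(0.934) = 0.792. Intervention, in the same way: 0.619. Mean 0.706.
- ρ = 0.706 / √(0.965 × 1.180) = 0.66. Residual variance = 1.180 − 0.706² / 0.965 = 0.663.
- Adjusted half-width: 1.985 × √(2 × 0.663 / 50) × √(1 + 1/96) = 0.325.
- Gain: (0.431 / 0.325)² = 1.76.

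*All cells.* Simulation with 8,000 trials per cell, t-test against regression on arm and randomization count, gave the half-widths below. The gain is the variance ratio.

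| In place at randomization | None lost | Gain | 15% lost | Gain | 30% lost | Gain |
|---|---|---|---|---|---|---|
| 5% | .394 → .374 | 1.11 | .392 → .380 | 1.06 | .389 → .383 | 1.03 |
| 10% | .405 → .364 | 1.24 | .401 → .376 | 1.14 | .397 → .384 | 1.07 |
| 20% | .422 → .345 | 1.50 | .417 → .370 | 1.27 | .410 → .385 | 1.13 |
| 30% | .431 → .325 | 1.76 | .427 → .363 | 1.38 | .420 → .386 | 1.18 |
| 50% | .423 → .277 | 2.33 | .432 → .349 | 1.53 | .431 → .388 | 1.23 |
| 60% | .409 → .250 | 2.68 | .427 → .341 | 1.57 | .434 → .389 | 1.24 |

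**Variations.**
- Toxicology and ECG never lost once ordered, 30% of the rest lost: gain 1.10–1.39 over 10–60% in place.
- As above, but benzodiazepine avoidance met in 80% by default and the other elements at 10/20/30%: 1.34/1.59/1.85 with no loss, 1.11/1.19/1.26 with 30% loss of the rest.

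**Bias and error rate.** The expected difference with no loss is 0.20 × (1 − s) × 4.45, which is 0.80 at 10% in place and 0.36 at 60%. Adjusted and unadjusted means agreed within 0.003. The fall is a ceiling effect that adjustment does not undo. With no true effect, both methods rejected in 4.8–5.3% of trials.

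**The case against.** The strongest points on the other side:

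1. **The window gap is narrow.** Four of the six named elements can be scored by status at discharge without a start. Only toxicology and ECG need one, and ECG applies only to patients on methadone. This stands as a limit on the definition point. It does not touch the missing covariate.
2. **Another window would remove most of the noise without adjustment.** If only elements newly met after randomization counted, the unadjusted half-widths at 10/20/30/50% in place would be .369/.355/.339/.298. That is close to the adjusted figures with no loss and better than them with 30% loss. But a count of new orders is not what a reading at discharge describes. It would also need each element's status at randomization, which is the missing item, and it suits benzodiazepine avoidance poorly.
3. **The rates are assumed and may be low.** This stands. Section 1.1 says generalists seldom prescribe in line with guidelines, and patients with an Addiction Medicine consult are excluded. At 5% in place with 30% lost, the average gain is 1.03 times, and the adjusted SE is larger in 30% of single trials.
4. **Adjusted regression is already allowed and order times stay in the chart.** Both are true, so nothing is irretrievable. But no covariate is named, the hospitalization characteristics to be abstracted are unspecified, and a covariate chosen after seeing imbalance is weaker than one fixed beforehand.
5. **It is a pilot.** This limits the importance of the point but does not argue against an inexpensive improvement.

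**Conclusion.** The concern holds. The start of the window is unstated, no care-element count at randomization is planned in both arms, and the main comparison is unadjusted. The consequence is lost precision on a secondary outcome. The planned comparison remains valid, and the primary feasibility outcomes are unaffected.

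Confidence that the gap exists is high. Confidence in the size of the gain is moderate, because it rests on assumed prior ordering, persistence and uptake. It ranges from almost nothing (1.03 times the patients, few elements in place and many lost) to large (2.7 times, most in place and none lost). From 10% in place upward, even with 30% lost, it is about 1.1–1.2 times. The average interval was narrower in every case examined. The change is worth making because it costs little.

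**What to change.** **Section 3.2.2, add:**
> In both arms, each element will be scored met or not met at randomization and at discharge from order times in the medical record, using the same abstraction form. One-time orders (urine toxicology, ECG) count if placed from the index admission up to that time point. Medication elements and benzodiazepine avoidance are scored by status at that time point. The outcome is the number of elements met at discharge.

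**Section 3.7.3, add:**
> The planned comparison for this outcome is a linear regression of the discharge count on arm and the count at randomization, reporting the difference with its 95% CI. The unadjusted comparison is supportive.

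**Section 4.6:** add the randomization time point to the abstraction form.

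Two cautions apply. The intervention team's chart review should not serve as the randomization count, because the control arm has none. A simple change score should not replace the regression: its variance is 2(1 − ρ) times the unadjusted variance, which is worse when ρ is below 0.5.

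The cost is wording in three sections and one more time point read from 100 charts already being abstracted. Sample size, visits and patient burden do not change. The downside is a little extra abstraction time, with little return if few elements are in place at randomization or many are lost by discharge.

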3.3 Study Population

The study population will be comprised of adult patients (≥ 18 years) hospitalized on medical units at YNHH YSC and SRC with chronic pain and opioid use. Eligible patients can be hospitalized for any medical condition (i.e., admission diagnoses do not need to be related to chronic pain). Patients will be identified by a pre-specified case identification tool (i.e., Epic report).

3.3.1 Number of Participants

We anticipate 10-50 records will be returned in the Epic report each day that will be screened for eligibility. We aim to recruit 100 participants who meet all inclusion and exclusion criteria for the trial, for a total of approximately 50 each in the intervention and control arms. Screening and enrollment will continue until the target sample size has been reached, with a goal of recruiting 5-10 patients per week.

Eligibility Criteria/Vulnerable Populations

In order to be eligible for inclusion in the study, an individual must meet all of the following criteria:

- adults (age ≥ 18 years);
- admitted at YNHH (YS and SRC) on medical units;
- identified as having chronic pain and prescribed opioids.
- Have opioid dependence (evidenced by ongoing opioid prescription, meeting DSM-5 criteria for OUD, or clinical history)

Any individual who meets any of the following criteria will be excluded from participation in this study:

- active cancer
- current pregnancy
- hospice care/comfort measures only
- admission to inpatient psychiatry
- completed or planned Addiction Medicine consult during hospitalization

4. Study Methods/Procedures

3.4 Study Procedures

All patients will receive standard hospital care. Patients who are identified as eligible for the study via screening in Epic will be approached during hospitalization, undergo informed consent, and be enrolled in the study. Those who consent will be asked questionnaires

related to patient reported outcomes of pain, anxiety, depression and quality of life at baseline. Patients will then be randomized on a 1:1 ratio to either the enhanced opioid stewardship program arm or a control (i.e., usual care) arm. Patients who are randomized to the intervention arm will have their medical record reviewed by both a pharmacist and a physician trained in pain and addiction medicine. The pharmacist and physician will provide best practice guidance via an Epic note to the primary care teams to consider, versus continuation with their usual care plan. All guidance will be voluntary for clinical teams to follow. All participants will be tracked daily in Epic for discharge status, and when discharge within 48 hours is anticipated, the study team will perform the final patient interview, which will be very similar to the baseline interview and composed of questionnaires related to pain, anxiety, depression, and quality of life. Medical record abstraction will be performed to abstract relevant characteristics of each participant's hospitalization, use of guideline-based best practices for pain management and opioid stewardship at discharge, and incidence of readmissions and ED visits within 30 days after discharge for the hospitalization during which the participant was recruited.

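### The plan does not say who conducts the final interview or scores the care-element count, and nothing keeps the allocation from them

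*Combined protocol and SAP*

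**What the plan says.** Section 3.4 assigns the last patient contact broadly: "the study team will perform the final patient interview". For the chart data it names nobody: "Medical record abstraction will be performed to abstract relevant characteristics of each participant's hospitalization". Section 3.2.2 says of the care elements only that "These metrics will be abstracted from the medical record".

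The order of events is in the table in Section 3.5. Step 5 is "Participant randomized to intervention or usual care arm"; the final interview is step 10 and the record abstraction is step 11. In between, at step 8, "Study addiction medicine physician composes note in intervention participant's medical record". Section 3.4 gives the comparator as usual care, and no matching note for that arm is described.

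The care elements in Section 3.2.2 are mostly orders, for example "ordering of a bowel regimen, ordering of medication to treat opioid use disorder, order of urine toxicology screen". The list closes with an unspecified category of other good practices. Section 3.6.3 makes pain, depression, anxiety and satisfaction interview questions answered by the participant.

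No section states that participants, interviewers, abstractors or analysts are kept unaware of the arm.

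**The concern.** An outcome collected after randomization by someone who may know the arm can differ between arms because of how it was collected. Two routes are open here.

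The first is the interview. Pain, PHQ-4 and satisfaction answers are given to a member of a team that is testing a directional hypothesis (Section 2.1). Prompting, probing or tone may differ by arm.

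The second is the chart. An abstractor working through the full record of an intervention participant will meet a note that sets out recommended care. No such cue exists in a control chart. With an open-ended item at the end of the list, there is room to credit more in one arm.

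Both routes would probably favour the intervention. Section 4.15 intends the findings as preliminary data for future grants and for a manuscript covering preliminary efficacy, so a biased difference could carry into the planning of a later trial.

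**Working it through.** **Who is shown to know the arm**

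| Task | Who, according to the protocol | Must know the arm? |
|---|---|---|
| Chart review, note and alert (3.4; 3.5, steps 7 to 9) | Study physician and pharmacist | Yes |
| Screening (3.6.1), approach and consent (3.6.2) | Research assistant, with the PI for screening | No, it precedes randomization |
| Randomization (3.5, step 5) | Not stated | Whoever does it learns the arm |
| Final interview (3.4; 3.5, step 10) | The study team, no role given | Not for the task itself |
| Abstraction (3.2.2; 3.4; 3.5, step 11) | Not stated | Not to score orders |

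The physician and pharmacist learn the arm because they act on one arm only: "Patients who are randomized to the intervention arm will have their medical record reviewed by both a pharmacist and a physician". Step 7 of Section 3.5 describes them as belonging to the study team, the same term that covers the final interviewer. As written, the plan would allow the author of the note to interview the participant and score the chart. It does not say that this will happen.

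**Illustration of size**

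The plan has no figure to reproduce. Section 3.7.2 declines a power calculation, and no SD, alpha or expected difference is given. Everything below except the planned 50 per arm (Section 3.3.1) is assumed.

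Inputs: SD 2.5 points, 45 completers per arm, two-sided 5% test, no true effect, and a collection bias of b points in one arm.

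- SE = 2.5 × √(2/45) = 0.53.
- Rejection probability = Φ(b/SE − 1.96) + Φ(−b/SE − 1.96).
- b = 0.3: b/SE = 0.57, probability 0.088.
- b = 0.5: b/SE = 0.95, probability 0.158.

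In SD units these biases are 0.3/2.5 = 0.12 and 0.5/2.5 = 0.20. The same formula with b/SE = (bias in SD) × √(n/2) gives the range:

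| Bias (SD) | 50 per arm | 40 per arm |
|---|---|---|
| 0 | 5% | 5% |
| 0.1 | 8% | 7% |
| 0.2 | 17% | 15% |
| 0.3 | 32% | 27% |

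Partial masking gives partial benefit. If it removed half of a 0.3 SD bias at 50 per arm, the rate would fall from 32% to about 12%, not to 5%.

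For the count, crediting one extra element in an assumed 20% of intervention charts adds 0.20 × 1 = 0.2 elements to the difference. Without an SD for the count, its effect on a test cannot be given.

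**The case against.** The strongest reply is that the case rests on silence. A reader might infer that the interviewer and abstractor know the arm, or are the same people. The documents do not say so. Only the physician and pharmacist are shown to know it. This stands, and the point is limited to the absence of any safeguard.

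The instruments also limit interviewer influence. Section 3.6.3 repeats the baseline pain, depression and anxiety questions unchanged and gives the satisfaction question word for word. Most named care elements are orders that are either present or absent. Both points stand and make large biases less likely. They do not cover how questions are asked and followed up, or the open-ended item.

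A reader might also infer that masking would remove the bias, and at no cost in staff. The documents support neither. Participants are not stated to be masked, the consent form describes the intervention in detail (Section 3.6), and the control is usual care, so bias from respondents themselves would remain. Staffing numbers are not given. Some tasks also need the arm or the recommendations: monitoring reactions to recommended treatments (Section 3.4.2) and reporting how many intervention participants received the full intervention (Section 3.2.1). The weekly data reviews (Sections 4.5 and 4.10) could expose the arm too. Access therefore cannot simply be restricted to the physician and pharmacist.

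Finally, these outcomes are secondary, the tests are exploratory, and no main efficacy outcome is designated. That lowers the stakes but does not remove them, given the intended use of the results.

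**Conclusion.** The concern holds in limited form. The protocol leaves the final interviewer and the abstractor unnamed, masks neither, and takes the care count from charts that carry a cue in one arm only. The secondary pain, PHQ-4, satisfaction and care-count outcomes are open to assessment bias, probably in favour of the intervention. Exposure is uneven: least for elements that are recorded orders, more for the open-ended item and the interview answers.

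The size is unknown. The 9% and 16% false-positive rates are illustrations under the assumed SD, completers, test and shifts, and should not be read as estimates for this trial.

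The primary feasibility outcomes are largely unaffected. The one qualification is completion of the peri-discharge evaluation, which could differ if staff who know the arm pursue one group harder.

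**What to change.** 1. State in Sections 3.4 and 3.5 who randomizes, who conducts the final interview and who abstracts the chart.
2. Before enrolment, replace the open-ended list in Section 3.2.2 with a closed list of elements and a scoring rule, including how to score an element that does not apply to a given patient. Score it in both arms from order and medication records, and complete it before any note is read.
3. Use REDCap permissions to hide the allocation from the final interviewer. The research assistant could fill this role if that person does not randomize. Keep the allocation visible to the physician, the pharmacist and those who need it for safety monitoring and delivery reporting.
4. After each final interview, record whether the interviewer had learned the arm. In the report, acknowledge that respondent bias in the self-reported outcomes remains.

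The cost is protocol wording, a checklist and database permissions. Whether existing staff can absorb the split of roles is for the investigators to confirm. The downside is imperfect masking, because the note sits in the chart and participants are tracked daily in Epic. That is the reason for recording unmasking.
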